### 1. ECHOCARDIOGRAM

A resting transthoracic echocardiogram will be performed with MyLab Alpha, ESAOTE, Italy. The exam will be performed by the echocardiography laboratory cardiologists, who will be blinded to experimental protocol and group randomization, with the usual measurements of systolic and diastolic function, particularly the calculation of left ventricular ejection fraction by Simpson's formula, telediastolic and telessystolic volumes and diameters, doppler analysis of the transmitral flow, tissue doppler and quantification of mitral valve regurgitation.

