## PURPOSE

To overcome the lack of knowledge regarding the physiological effects after hospital-based CR program, a 12 month RCT study will be performed. This study will hopefully contribute to generate evidence-based exercise prescription approaches to prolong the ET after the end of hospital-based CR programs.

The purpose of this research project is twofold:

1) To conduct a 12-month randomized control trial to evaluate the effects of periodized ET regime versus a non periodized ET regime on VO2 peak, maximal strength, body composition, functionality and quality of life in CVD patients.

2) to differentiate the effects of a 12-month periodized ET regime versus a non periodized ET regime on the different components of the oxygen kinetics response and oxidative adaptations in CVD patients.

The primary end points for aim 1 are: cardiopulmonary exercise testing (CPET) variables such as VO2 peak, AT, peak work rate, ventilatory equivalent of carbon dioxide (VE/VCO2), ventilatory equivalent of oxygen (VE/VO2), minute ventilation (VE), one repetition maximum (1RM), total body bone mineral content, lean and fat tissue mass and percentage of body fat mass, quality of life and functional physical fitness tests. The primary end points for aim 2 are oxygen kinetics and muscle deoxygenation dynamics of the vastus lateralis muscle at the submaximal test.

The hypothesis for this study are: 1) considering that this type of periodization exerts higher stress on the cardiovascular and neuromuscular systems, so that there could be greater adaptations, leading to higher increases in VO2max, muscle strength, body composition and functionality compared to non periodized ET regime; 2) there will be a better improvement microvascular O2 delivery in the exercise transient in response to periodized ET regime that would be associated with a faster adjustment of pulmonary VO2 kinetics than in non periodized group. Improvements in microvascular O2 delivery would be indicated by a better matching between the rate of adjustment of muscle deoxygenation relative to phase II pulmonary VO2, which represents a decreased reliance on O2 extraction for a given pulmonary VO2.

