## STUDY DESIGN

A longitudinal RCT research design using two distinct ET prescriptions (periodization vs non periodization) will be applied in CVD patients. Briefly, following the informed consent process, patients will be randomized and stratified (by gender and age) to periodization or non periodization groups. The randomization code will be developed with a computer random-number generator to select random permuted blocks. Participants will exercise for a period of 12 months. All the same assessments, except the echocardiogram that will be done in M0 and M3 (for risk stratification), are going to be taken in 4 different time points during a year: M0 - baseline, M1 - 3 months after starting the ET, M2 - 6 months after starting the ET and M3 - 12 months after starting the ET. The patients will be randomized into either one of the two ET groups. Recruitment and screening will last 12 months (September 2017 to September 2018) and the patient assessment will last until September 2019. It is expected to finish the project with peer-review redaction submitted and/or accepted in December 2019.

The following assessments on the 4 time points will be performed at the Pulido Valente Hospital, FMH-UL and Academia de Fitness at EUL: Echocardiogram (Echo) (MyLab Alpha, ESAOTE); cardiopulmonary exercise test (CPET) (Ergostik, Geratherm Respiratory GmbH, Bad Kissingen); skeletal muscle deoxygenation dynamics (NIMO, Nirox srl); body composition - dual energy radiographic absorptiometry (DXA, Hologic Explorer-W); objective measured physical activity - accelerometer (ActiGraph GT3X+); functional physical fitness - Fullerton Functional Fitness Test; isometric strength – portable hand dynamometer JAMAR plus digital (Sammons Preston); maximal strength – 1RM and Quality of Life questionnaire.

All assessment moments will be done in 1 to 2 weeks:

Day 1 – Echo and CPET will be performed at the Pulido Valente Hospital;

Day 2 and 3 – during the day and time of the ET session at the EUL, the patient will perform: functional physical fitness tests; maximal strength; isometric strength and Quality of Life questionnaire;

Day 4 – In FMH, the dual energy radiographic absorptiometry (DXA) exam and the activation of the accelerometer to measure the objective measured physical activity will be done.

Day 5 – Submaximal CPET with the skeletal muscle deoxygenation dynamics at the Pulido Valente Hospital.

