### EXPECTED RESULTS

The variables measured in this task will provide clinical information to patient screening. Most of the human and animal studies demonstrated that post-MI physical exercise training results in positive effect on myocardial remodeling. These beneficial effects include improved cardiac function, mitigated interstitial myocardial fibrosis, and enhanced physical capacity. It is expected a positive effect on myocardial remodeling in both exercise training groups. It is important to note that the existing studies have only investigated the effects of endurance exercise on post-MI remodeling; therefore, the effects of post-MI resistance training or combined endurance and resistance training have yet to be systematically examined to identify a better exercise mode.

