#### ***Symptom-limited exercise test***

A symptom-limited ramp incremental CPET, in accordance with the Clinician's Guide to Cardiopulmonary Exercise Testing in Adults, will be performed on a cycle ergometer (Ergostik, Geratherm Respiratory GmbH, Bad Kissingen, Germany) with breath-by-breath gas exchange measurements. Gas exchange analysis provides a highly reproducible measurement of exercise limitation and insights into the differentiation between cardiac or respiratory cause of dyspnea, assesses ventilator efficiency and carries prognostic information. After 2 minutes rest followed by 2 minutes unloaded pedaling and 2 more minutes at rest, each patient will be encouraged to exercise to exhaustion (20 Watt+20 Watt/min or 15 Watt+15Watt/min or 10 Watt+10 Watt/min), as defined by intolerance, leg fatigue or dyspnea unless clinical criteria for test termination occurred. Patients will continue seated on the cycle ergometer as soon as they stop, while recovery measurements are taken. Twelve-lead ECG will be recorded continuously and blood pressure will be recorded at baseline, every two minutes, at peak exercise and during recovery. Peak oxygen capacity will be considered the highest attained  $\text{VO}_2$  during the final 30s of exercise and ventilator AT will be estimate by the V-slope method. HR recovery as a simple marker of parasympathetic activity will be calculated as the difference between peak HR and HR one minute later. The recovery period will continue until 6 minutes after peak effort. Chronotropic response (CR) to exercise will be evaluated by the % of HR reserve (HRR) used at peak exercise.  $\text{CR} = [\text{peak HR} - \text{resting HR} / (220 - \text{age} - \text{resting HR}) \times 100]$ . A failure to use 80% of the HRR is defined as chronotropic incompetence. All patients should achieve a respiratory exchange ratio of  $>1.1$ , an indicator of

maximal effort in the CPET. The CPET will provide clinical information to patient screening and exercise intensity prescription.

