## 12. DATA BASE MANAGEMENT AND REPORTS

This task includes the treatment of the variables obtained during the data collection period. In order to assure the confidentiality of the participants an ID code will be attributed to each participant in the database and all the equipment's and sheets used. A single researcher will perform the database management.

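### Assessor blinding is stated only for the echocardiogram; none is stated for the CPET operators, the AT reader or the kinetics analyst, who produce primary endpoints

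*Combined protocol and SAP*

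**What the plan says.** **Where blinding is stated.** Section 1 (Echocardiogram) says that the exam is done by laboratory cardiologists "who will be blinded to experimental protocol and group randomization". The documents contain no other blinding or masking statement.

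**What the echocardiogram is for.** Study Design excludes it from the common schedule: "except the echocardiogram that will be done in M0 and M3 (for risk stratification"). The Expected Results under Section 1 say: "The variables measured in this task will provide clinical information to patient screening". They also say: "It is expected a positive effect on myocardial remodeling in both exercise training groups". That is an expectation for both arms, with no between-arm hypothesis. The Purpose section does not list echo among the primary endpoints.

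**What the primary endpoints are.** For aim 1, Purpose lists "cardiopulmonary exercise testing (CPET) variables such as VO 2 peak, AT, peak work rate" and further items. For aim 2 it lists oxygen kinetics and vastus lateralis deoxygenation in the submaximal test.

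**How those endpoints are obtained.** In the symptom-limited test "each patient will be encouraged to exercise to exhaustion". VO2 peak is the highest value in the last half-minute, AT is estimated by V-slope, and an RER above 1.1 is given as the sign of maximal effort. The submaximal test is repeated three times, averaged and curve-fitted in software. The operator, reader and analyst are not identified.

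**Setting.** On Day 1, "Echo and CPET will be performed at the Pulido Valente Hospital". The submaximal test is at the same hospital on Day 5. Section 12 says that "an ID code will be attributed to each participant in the database"; the stated reason is confidentiality.

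**The concern.** Patients and trainers in an exercise trial know the allocation, so protection against expectation bias rests on the assessors. Here the stated protection covers a measurement outside the primary endpoint list, and none is stated for the measurements that decide the trial.

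The risk has a direction. The Expected Results for the CPET and for muscle deoxygenation both anticipate the larger gains in the periodized arm. An operator who knows the arm may encourage harder, and a reader who knows the arm may settle an ambiguous threshold or fit differently. Either would move the contrast towards the hypothesis. The statistical analysis section has no check for this. The team also meets every two months to discuss patients' progress (Study Design), and nothing says that allocation is kept from those who test or read.

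**Working it through.** **Step 1. Blinding set against endpoint role**

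| Measurement | Listed primary endpoint? | Where judgement enters | Blinding stated? |
|---|---|---|---|
| Echocardiogram | No (risk stratification, screening) | Reader | Yes |
| VO2 peak, peak work rate | Yes, aim 1 | Encouragement; moment of stopping | No |
| AT | Yes, aim 1 | V-slope reading; whether it can be determined at all | No |
| VO2 and HHb kinetics | Yes, aim 2 | Curve fitting | No |

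**Step 2. How the AT reading carries forward.** The submaximal load is 80% of the work rate at AT, or is based on 50% of VO2 peak if AT cannot be determined. The AT reading therefore also affects the conditions under which the aim 2 endpoints are measured. In Section 10 the periodized arm's intensity is set from AT1 and AT2 where they can be determined, while the comparator's is expressed in %HRR. The AT result must therefore leave the laboratory, tied to the patient and visit. Allocation need not come back in.

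**Step 3. Size, on an assumed bias.** The plan gives no figure for measurement bias. Its design inputs (Participants section) are a difference of 3 ml/kg/min, SD 3.5, alpha 0.05, power 0.80, dropout 37% and 25 per arm. The stated total of 50 can be reproduced with a one-sided t-test: d = 3/3.5 = 0.857 needs 18 per arm, and 18 × 1.37 = 24.7, so 25 per arm. The sidedness is not stated, and the present point does not depend on it.

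Assume a between-arm differential b of 0.5, 1.0 or 1.5 ml/kg/min in measured VO2 peak. As a share of the design difference:

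- 0.5/3 = 17%
- 1.0/3 = 33%
- 1.5/3 = 50%

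With no true difference, the chance of a significant two-sided 0.05 t-test is P(|T| > t-critical). T is noncentral t with 2n − 2 degrees of freedom and noncentrality (b/3.5) × √(n/2). For b = 1.0 and n = 25 the noncentrality is 0.286 × 3.536 = 1.01. After 37% dropout, 25 × 0.63 = 15.75, taken as 16 per arm.

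| Assumed b (ml/kg/min) | False-positive rate, 25 per arm | False-positive rate, 16 per arm |
|---|---|---|
| 0.5 | 7.9% | 6.8% |
| 1.0 | 16.8% | 12.3% |
| 1.5 | 31.8% | 21.7% |

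These rates show sensitivity to an assumed bias. They do not estimate the bias in this trial.

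**The case against.** The strongest reply is that the tests already limit discretion. RER above 1.1 guards against submaximal effort, VO2 peak follows a fixed rule, and the kinetics are fitted by software to the average of three repeats. This stands in part. The RER criterion is worded as something patients should reach, no consequence of missing it is given, and effort can still differ above 1.1. It does nothing for AT reading or curve fitting. These safeguards narrow the room for bias but do not replace masking.

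Several stronger readings are tempting, and the documents do not support them:

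- **That blinding could be extended at no staff cost.** The documents do not say who runs or reads the CPET, or what staff and budget exist. A shared hospital makes extension plausible, no more.
- **That the CPET always accompanies the blinded echo.** Echo is done only at M0 and M3, so M1 and M2 have the CPET without it. The submaximal test is on another day.
- **That AT should be read blind to visit.** AT is needed between Day 1 and Day 5 of the same visit to set the submaximal load, and afterwards for training intensity. Visit masking would need a second, later reading of every test.
- **That the assessors are known to be unblinded, or the results biased.** Blinding is not stated. It may be intended.
- **That all these endpoints depend on effort.** This applies mainly to VO2 peak and peak work rate.

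It is also fair to say that 1RM, the functional tests and SF-36 are primary for aim 1 and carry no blinding statement either. The first two are tested at the training site in the session slot, where independent assessors could need extra staff. That is why this point is confined to the hospital CPET and its off-line reading.

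**Conclusion.** The point holds as a gap in stated protection. Blinding is written only for a measurement that is not a listed primary endpoint. It is not stated for the operators, reader and analyst behind VO2 peak, AT and the VO2/HHb kinetics, in a trial whose investigators expect one arm to do better. As written, the plan leaves these endpoints open to unequal encouragement and unequal reading.

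The size is unknown. The range of 17% to 50% of the design difference, and the false-positive rates above, follow from an assumed differential of 0.5 to 1.5 ml/kg/min, the plan's SD of 3.5 and a two-sided test. Neither the presence nor the amount of bias can be inferred from the documents. The change is worth making because it is cheap and affects no sample size, alpha, visit or treatment.

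**What to change.** 1. Use one scripted encouragement protocol, identical for every patient, at every maximal CPET.
2. Extend the Section 1 echo wording to the hospital CPET: allocation is not disclosed to the CPET operators, where existing staffing allows.
3. Have AT and the VO2/HHb kinetics read from files that carry only the ID code, without the arm. Keep the patient and visit link needed to set the submaximal load and training intensity. Report the same threshold values for every patient, so that the request itself does not reveal the arm.
4. Report peak RER by arm at each visit as a check on equal effort. It can show unequal effort but does not correct for it.

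If such masking is already intended, stating it settles items 2 and 3.

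The cost is some administration, and patients will occasionally disclose their arm. Whether any extra staff time is needed cannot be judged from the documents.

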### EXPECTED RESULTS

The variables measured in this task will provide clinical information to patient screening. Most of the human and animal studies demonstrated that post-MI physical exercise training results in positive effect on myocardial remodeling. These beneficial effects include improved cardiac function, mitigated interstitial myocardial fibrosis, and enhanced physical capacity. It is expected a positive effect on myocardial remodeling in both exercise training groups. It is important to note that the existing studies have only investigated the effects of endurance exercise on post-MI remodeling; therefore, the effects of post-MI resistance training or combined endurance and resistance training have yet to be systematically examined to identify a better exercise mode.

### 2. CARDIOPULMONARY EXERCISE TEST

CPET is the best technique to obtain the maximal and submaximal functional capacity. Those tests will be performed with the subjects in a non-fasting condition and under the regular medication.

#### ***Symptom-limited exercise test***

A symptom-limited ramp incremental CPET, in accordance with the Clinician's Guide to Cardiopulmonary Exercise Testing in Adults, will be performed on a cycle ergometer (Ergostik, Geratherm Respiratory GmbH, Bad Kissingen, Germany) with breath-by-breath gas exchange measurements. Gas exchange analysis provides a highly reproducible measurement of exercise limitation and insights into the differentiation between cardiac or respiratory cause of dyspnea, assesses ventilator efficiency and carries prognostic information. After 2 minutes rest followed by 2 minutes unloaded pedaling and 2 more minutes at rest, each patient will be encouraged to exercise to exhaustion (20 Watt+20 Watt/min or 15 Watt+15Watt/min or 10 Watt+10 Watt/min), as defined by intolerance, leg fatigue or dyspnea unless clinical criteria for test termination occurred. Patients will continue seated on the cycle ergometer as soon as they stop, while recovery measurements are taken. Twelve-lead ECG will be recorded continuously and blood pressure will be recorded at baseline, every two minutes, at peak exercise and during recovery. Peak oxygen capacity will be considered the highest attained  $\text{VO}_2$  during the final 30s of exercise and ventilator AT will be estimate by the V-slope method. HR recovery as a simple marker of parasympathetic activity will be calculated as the difference between peak HR and HR one minute later. The recovery period will continue until 6 minutes after peak effort. Chronotropic response (CR) to exercise will be evaluated by the % of HR reserve (HRR) used at peak exercise.  $\text{CR} = [\text{peak HR} - \text{resting HR} / (220 - \text{age} - \text{resting HR}) \times 100]$ . A failure to use 80% of the HRR is defined as chronotropic incompetence. All patients should achieve a respiratory exchange ratio of  $>1.1$ , an indicator of

maximal effort in the CPET. The CPET will provide clinical information to patient screening and exercise intensity prescription.

### ***Submaximal exercise test***

On a separate day to the maximal test, patients will be recruited for a constant load exercise test. The test load is set at 80% of the value of the work rate corresponding to the AT detected in the maximum test, which was performed first, or 50% of VO2 peak, if the AT could not be adequately determined. Cardiopulmonary data will be recorded for 5 minutes at rest followed by 1 minute unloaded pedaling. After unloaded pedaling, patients will perform the constant load test for 6 min at the work rate described above, followed by unloaded pedaling for 5min. To improve the confidence of the kinetic parameter determination, this test will be performed three times and the averaged profile will be used for the kinetic analysis.

Curve fitting will be performed with Graphics software Origin version 7.0 (Microcal Software Inc., Northampton, Massachusetts, USA) using iterative techniques. The kinetics of the oxygen uptake response to the constant workload exercise will be analyzed by the sequent separate phases.

Before each maximal and submaximal test, the gas analyzer will be calibrated using ambient air and standard calibration gases of known concentration (16.7% O2 and 5.7% CO2). The calibration of the turbine flowmeter will be performed using a 3l syringe (Quinton Instruments, Seattle, Wash.) Twelve-lead ECGs, blood pressure, and ratings of perceived exertion will be recorded during each exercise stage.

## EXPECTED RESULTS

---

The CPET will provide fundamental information to exercise intensity prescription and is a primary endpoint for purpose 1 and 2. We expect increases in VO2max in both training regimes from 5%–15% after 12 months of physical conditioning, with the greatest improvements in the periodized training group.

It is expected that there would be an improved microvascular O2 delivery in the exercise transient in response to both training groups that would be associated with a faster adjustment of VO2 kinetics, with the greatest improvements in the periodized training group.

---

## 3. SKELETAL MUSCLE DEOXYGENATION DYNAMICS

The muscle deoxygenation dynamics of the Vastus Lateralis muscle will be evaluated throughout the submaximal CPET. Deoxyhaemoglobin [HHb], oxyhaemoglobin [HbO2], and total haemoglobin [HbT] concentrations will be quantified with a continuous-wave tissue oximeter (NIMO, Nirox srl, Brescia, Italy), based on the Near-infrared Spectroscopy (NIRS) system, which provides continuous, non-invasive monitoring of the relative concentration changes in these variables during rest and exercise. Briefly, this system is based on the oxygen dependency of absorption changes for near infra-red light in haemoglobin and myoglobin and it consists on an emission probe which emits three wave lengths (685, 850 and 905 nm) and a photon detector. The intensity of incident and transmitted light will be record continuously at 40 Hz and used to estimate the concentrations changes relative to baseline for oxygenated, deoxygenated and total haemoglobin. To account for the possible influence of the local fat layer on NIRS a real-time correction using an algorithm included in the software program v2.0 supplied with the spectrometer (Nimo Data Analysis Peak) will be used. Since the HHb signal is less dependent of changes in blood flow it can be used as an indicator of fractional O2 extraction within the microvascular level. This task will be performed at rest, during and immediately following the

submaximal CPET. The off- oxygen consumption and HHb kinetics will be determined using a monoexponential model which incorporates an amplitude, time constant and time delay.

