#### EXPECTED RESULTS

---

The off- oxygen consumption and HHb kinetics will be determined using a mono-exponential model which incorporates an amplitude, time constant and time delay. As the recovery of muscle and total body oxygenation from both maximal and submaximal exercise is delayed in sedentary participants, it is expected that the exercise training, in particular the periodized training group, induces a decrease of the time constant of the exponential decrease of these parameters.

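### Hypothesis 2 concerns matching of muscle deoxygenation to phase II VO2 at exercise onset, but the only HHb kinetic model stated reads as a recovery model and no matching index is defined

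*Combined protocol and SAP*

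**What the plan says.** All references are to the combined protocol and SAP.

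- **Purpose, endpoints.** "The primary end points for aim 2 are oxygen kinetics and muscle deoxygenation dynamics of the vastus lateralis muscle at the submaximal test". No phase, parameter or derived index is named.
- **Purpose, hypothesis 2.** The prediction is that "there will be a better improvement microvascular O 2 delivery in the exercise transient in response to periodized ET regime". The indicator given for it is "a better matching between the rate of adjustment of muscle deoxygenation relative to phase II pulmonary" VO2, interpreted as less dependence on extraction at a given VO2.
- **Section 2, Submaximal exercise test.** Six minutes at constant load are followed by five minutes of unloaded pedalling. For VO2, "The kinetics of the oxygen uptake response to the constant workload exercise will be analyzed by the sequent separate phases". The phases are not listed and no equation is given.
- **Section 2, Expected Results.** The same expectation is repeated, with improved "delivery in the exercise transient in response to both training groups that would be associated with a faster adjustment of VO 2 kinetics".
- **Section 3, Skeletal muscle deoxygenation dynamics.** NIRS recording covers rest, exercise and the period just after it. The kinetic analysis is: "The off- oxygen consumption and HHb kinetics will be determined using a monoexponential model which incorporates an amplitude, time constant and time delay".
- **Section 3, Expected Results.** The model sentence is repeated. Its rationale is that recovery of oxygenation is delayed in sedentary people, and the prediction is that training "induces a decrease of the time constant of the exponential decrease of these parameters".
- **Section 13, Statistical analysis.** Means are to be compared for all outcomes. No kinetic parameter is named.

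**The concern.** The hypothesis and the HHb analysis appear to concern different parts of the test. Hypothesis 2 is about how delivery keeps up with uptake when the load is applied. The stated HHb model describes how the signal returns towards baseline when the load is removed. An analyst who follows section 3 literally would report recovery amplitudes, time constants and delays, and would not have the quantity that the Purpose section says will indicate improved microvascular delivery.

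HHb dynamics form part of the primary endpoint of one of the trial's two aims. If the test quantity is not fixed in advance, its form has to be decided during analysis, and a reader cannot tell whether the reported parameter was the intended one.

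**Working it through.** The plan states no figure on this point, so the check sets the passages side by side.

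**Step 1: what a test of hypothesis 2 needs.** From the indicator in Purpose, three components:

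- (a) phase II VO2 kinetics after the load is applied;
- (b) HHb kinetics over the same transient;
- (c) a rule that combines (a) and (b) into one measure of matching.

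The documents say exercise transient, not on-transient. On-transient is my reading. It rests on the references to adjustment and to phase II, and on the contrast with the off-kinetics in section 3.

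**Step 2: what the plan supplies.**

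| Component | Where addressed | Status |
|---|---|---|
| (a) phase II VO2 | Section 2, Submaximal exercise test | Partly: phase-by-phase analysis is planned, but phases and model are not given |
| (b) on-transient HHb | Nowhere explicit; section 3 models what reads as off-kinetics | Not specified |
| (c) matching index | Nowhere; the idea is in Purpose, the calculation is not | Not specified |

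So one component of three is partly specified and two are not.

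**Step 3: what the section 3 model yields.** Two signals (VO2 and HHb) with three parameters each (amplitude, time constant, delay) give 2 × 3 = 6 quantities. If the off prefix covers both signals, all six describe recovery.

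**Step 4: could the recovery parameters stand in for the index?** The section 3 prediction is that the recovery time constants fall. Matching is a relation between two signals. Suppose that it were expressed as τ(HHb)/τ(VO2), and that training multiplied the two constants by factors a and b, both below 1. The ratio would then change by a/b, which can be above, below or equal to 1. The predicted fall in both constants is therefore compatible with better, worse or unchanged matching. The constants also belong to a different transient from the one in the hypothesis.

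**Step 5: are the data there?** Yes. Section 3 records NIRS through rest, exercise and recovery, and section 2 includes a six-minute constant-load period. An on-transient fit needs no additional test.

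**The case against.** The strongest reply is that this is a brief protocol with detail left out, and not one aimed at the wrong quantity. The Purpose section names the indicator in advance, section 2 plans a phase analysis of VO2, and HHb is recorded throughout. Most of this stands. A reader might infer that hypothesis 2 cannot be tested in this trial. The documents do not support that, because the recordings would allow the fit and the index.

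A second reply is that the off prefix in section 3 may attach to oxygen consumption alone, which would leave HHb kinetics unrestricted. The grammar permits this. The Expected Results under section 3 count against it: they refer to recovery of both muscle and whole-body oxygenation, and to an exponential decrease in both parameters. Even on the narrower reading, no HHb-to-VO2 index is defined.

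A third reply is that the recovery and onset expectations can coexist. They can. Off-kinetics are a legitimate outcome, and nothing in the documents requires them to be secondary. A reader might also infer that the wording invites a selective choice of endpoint. That goes too far: hypothesis 2 is tied in advance to its indicator, so reporting recovery constants in its place would be a visible departure.

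What these replies do not answer is that no explicit on-transient HHb fit and no matching index are stated, while the model, rationale and prediction that section 3 does state all point to recovery.

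**Conclusion.** The point holds as a mismatch between hypothesis and analysis. Followed as written, the HHb analysis produces recovery parameters that do not test hypothesis 2, on a primary endpoint of aim 2. In size, two of the three components of the test quantity are unspecified and the third is only partly specified. No numerical effect on power or bias can be derived from the documents, and none is claimed.

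The conclusion rests on two readings: that exercise transient means the response to application of the load, and that the off prefix covers HHb as well as VO2. The first is well supported by the Purpose wording. The second is supported by the Expected Results under section 3. If the second reading failed, the missing index would remain.

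The correction should be made, but the point does not call the data collection into question.

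**What to change.** In section 3, make these changes:

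1. State that HHb and phase II VO2 are both fitted over the on-transient of the constant-load test, and give the model and fitting window for each. Say whether HHb traces are averaged over the three repeats, as section 2 plans for the test profile.
2. Pre-specify one matching index that tests hypothesis 2. One example is the normalised HHb-to-VO2 ratio over the on-transient. This is a suggestion and does not come from the documents; the sponsor may prefer another index, provided that it is single and fixed in advance.
3. State how the off-kinetics rank relative to that index. Either order can be defended if it is written down.
4. Align the Expected Results under section 3, so that the predicted change in the matching index appears alongside the recovery prediction. Name the index in section 13 as the quantity analysed for hypothesis 2.

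The cost is a few sentences of text and additional curve fitting on recordings already made. No extra tests, visits or patients are needed.
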